4. INVESTIGATIONAL PLAN

4.1. Overall Study Design

This is a Phase 2, open-label, 2-cohort study designed to evaluate the efficacy and safety of 2 INCB050465 treatment regimens in relapsed or refractory MCL previously treated either with or without a BTK inhibitor (see Figure 1). A total of approximately 190 subjects were planned to be enrolled across 2 cohorts. Cohort 1 will be closed to further enrollment by Protocol Amendment 7 with approximately 50 subjects enrolled. The estimated total number of subjects to be enrolled in the study is approximately 150.

Subjects with MCL who have received at least 1 but no more than 3 prior systemic treatment regimens will be screened for eligibility. Subjects will be allocated to Cohort 1 or Cohort 2 as follows:

- Cohort 1: Subjects have previously received ibrutinib
- Cohort 2: Subjects have not previously received a BTK inhibitor

Cohort 1 and Cohort 2 will have separate designs, conduct, and analyses.

The first 60 subjects in each cohort who meet the eligibility criteria will be randomly allocated to 1 of 2 study treatment regimens through the IWRS (see Section 5.1):

- Treatment A: INCB050465 20 mg QD for 8 weeks followed by 20 mg once weekly
 - Subjects in Cohort 1 receiving Treatment A will be referred to as Cohort 1A
 - Subjects in Cohort 2 receiving Treatment A will be referred to as Cohort 2A
- Treatment B: INCB050465 20 mg QD for 8 weeks followed by 2.5 mg QD
 - Subjects in Cohort 1 receiving Treatment B will be referred to as Cohort 1B
 - Subjects in Cohort 2 receiving Treatment B will be referred to as Cohort 2B

To better understand the safety and efficacy of INCB050465, a total of 70 additional subjects (30 subjects in Cohort 1 and 40 subjects in Cohort 2) will be enrolled into one of the 2 treatment regimens (A or B) being evaluated in this study. The treatment regimen will be selected after enrollment is completed for either Cohort 1 or Cohort 2 (ie, 60 subjects enrolled) and after evaluation of emerging safety and efficacy data from this and other monotherapy studies of INCB050465 in NHL. Once a treatment regimen is selected, the nonselected treatment regimen will be closed to further enrollment. Subjects receiving the nonselected treatment regimen may

switch to the selected treatment regimen or remain on their current treatment regimen, provided they have not met study treatment withdrawal criteria, and there are no safety concerns for their current treatment regimen. There will be no re-baselining for subjects who switch treatment regimens, and all subjects will continue to follow the same assessment schedule.

NOTE: The primary, secondary, [REDACTED] objectives and endpoints described in Section 2 are applicable for both cohorts; however, the cohorts will be analyzed separately, when applicable, as detailed in Section 9.

Subjects will receive treatment until disease progression, death, unacceptable toxicity, or consent withdrawal, whichever occurs first.

[figure not shown]
Subjects will be monitored for safety and efficacy periodically until disease progression, death, unacceptable toxicity, or withdrawal of informed consent. An IDMC will review safety data periodically as stated in the IDMC charter. Subjects will be evaluated for ORR by an IRC, and followed for DOR, PFS, and OS.

An interim futility analysis is planned for each of the cohorts when 30 subjects have been treated and have been evaluated for response or have permanently discontinued study treatment because of disease progression, withdrawal of consent, or death. Cohort 1 will be terminated for futility if ≤ 3 of the 30 subjects responded (ie, CR or PR) based on assessments provided by the IRC. Cohort 2 will be terminated for futility if ≤ 10 of the 30 subjects have responded (ie, CR or PR) based on assessments provided by the IRC. A timely assessment of response will be performed to avoid the risk of overenrollment.

The IDMC determined that the futility boundary was not crossed at the interim analysis of Cohort 1 and that there were no safety issues preventing further enrollment. However, the sponsor has concluded that the observed ORR is not clinically meaningful. Therefore, Cohort 1 will be closed to further enrollment by Protocol Amendment 7 with approximately 50 subjects enrolled. Subjects already enrolled in Cohort 1 will continue to receive study treatment per protocol.

After treatment discontinuation, subjects will be followed for safety and survival. Subjects who have discontinued study treatment due to reasons other than disease progression will be followed for radiologic disease progression, the start of a new anticancer therapy, or death, whichever comes first. It is expected that the final analysis will occur no later than 2 years after the first dose of INCB050465 is administered to the last subject treated.

Figure 1: Study Design of INCB 50465-205

4.2. Measures Taken to Avoid Bias

This is an open-label study; no comparisons will be made between subjects or against historical controls. Measurements of safety and efficacy are objective measurements, and only comparisons to pretreatment conditions will be made. Safety will be objectively assessed using NCI CTCAE v4.03 (NCI 2010) guidelines and reviewed by the IDMC. Tumor response will be assessed by an IRC using the CT-based criteria of the Lugano classification (Cheson et al 2014).

4.3. Number of Subjects

4.3.1. Planned Number of Subjects

The study was planned to enroll approximately 190 subjects at approximately 100 investigative sites globally. Cohort 1 will be closed to further enrollment by Protocol Amendment 7 with approximately 50 subjects enrolled. The estimated total number of subjects to be enrolled in the study is approximately 150.

4.3.2. Replacement of Subjects

No subjects will be replaced at any time during this study.

4.4. Duration of Treatment and Subject Participation

After signing the ICF, screening assessments may be completed over a period of up to 28 days. Each subject enrolled in the study may continue to receive study treatment in continuous 28-day intervals. If the subject discontinues study treatment, the treatment period will end, and the subject will enter the 30 to 35-day safety follow-up period, after which the subject will enter the survival follow-up period (see Section 6.4.3). Subject participation is expected to average approximately 26 months.

4.5. Overall Study Duration

The study begins when the first subject signs the ICF. The end of the study will occur when **all** subjects have discontinued from the study (see Section 5.7) **or** have completed at least 24 months of study participation (starting from the first dose of study treatment). It is estimated that the study will take approximately 2 years to accrue 150 subjects and that the final analysis will be performed no later than 2 years after the first dose of study treatment is administered to the last subject treated. Subjects who are still on study treatment and who have no evidence of progressive disease at the end of the study will have the option to continue on monotherapy with INCB050465 provided within a rollover Protocol, as local law permits (see Section 5.8).

4.6. Study Termination

The investigator retains the right to terminate study participation at any time for appropriate medical or organizational reasons. The investigator is to notify the institutional review board (IRB)/independent ethics committee (IEC) in writing of the study's completion or early termination, send a copy of the notification to the sponsor or sponsor's designee, and retain 1 copy for the site study regulatory file.

The sponsor may terminate the study electively, if required by a regulatory decision, or upon advice of the IDMC. If the study is terminated prematurely, the sponsor will notify the investigators, the IRBs and IECs, and regulatory bodies of the decision and reason for termination of the study. The IDMC will recommend termination of the study if warranted, as described in the IDMC charter (see also Section 9.5).

5. TREATMENT

5.1. Treatment Assignment

5.1.1. Subject Numbering and Treatment Assignment

Study sites will enter subject demographic and baseline data into the IWRS in order to receive a subject number and random treatment allocation.

All subject numbers will be 6 digits; the first 3 digits will be the site number, and the last 3 digits will be the subject's number. This subject number will be maintained throughout the study and will not be reassigned. Subjects who withdraw consent or discontinue from the study after being assigned a subject number will retain their initial number.

Site staff will contact the IWRS to allocate the subject to treatment assignment and obtain the initial study treatment assignment. The investigator or designee will select the assigned bottles of study treatment from their stock that correspond to the number provided by the IWRS and dispense the study treatment to the subject. All subsequent dispensing of study treatment should follow this process. Refer to the IWRS Manual for detailed information.

If a subject is mistakenly given a bottle of study treatment that is not the bottle assigned by the IWRS, the IWRS help desk must be notified immediately. The reason for the misallocation of the study treatment must be documented by the study site and reported to the IRB/IEC.

For subjects who signed an ICF but are not allocated study treatment and for subjects who are allocated study treatment but were not treated, refer to the eCRF Completion Guidelines for instruction on which eCRFs to complete.

5.1.2. Randomization and Blinding

Not applicable.

5.2. INCB050465

5.2.1. Description and Administration

Details of INCB050465 are shown in [Table 2](#).

Table 2: Description and Administration of INCB050465

Compound Name	INCB050465
Dose strengths	1 mg, 2.5 mg, 5 mg, and 20 mg
Form	Tablet
Active compound	INCB050465
Route of administration	Oral
Dose and regimen for Treatment A	20 mg QD for 8 weeks followed by 20 mg once weekly
Dose and regimen for Treatment B	20 mg QD for 8 weeks followed by 2.5 mg QD
Instructions	INCB050465 will be taken orally with water without regard to food [REDACTED] INCB050465 should be taken at approximately the same time each day.

For QD administration, if a dose is missed by more than 12 hours, then the subject should skip the dose and take the next scheduled dose at the usual time. For once-weekly administration, if the dose is missed by more than 2 days, then the subject should skip the dose and take the next scheduled dose.

5.2.2. Supply, Packaging, and Labeling

INCB050465 will be provided as 1 mg, 2.5 mg, 5 mg, and 20 mg tablets packaged in high-density polyethylene bottles. No preparation is required.

All Incyte investigational product labels will be in the local language and will comply with the legal requirements of each country.

5.2.3. Storage

Bottles of INCB050465 should be stored at ambient conditions (15°C-30°C or 59°F-86°F).

5.2.4. Instruction to Subjects for Handling INCB050465

The subject must be instructed in the handling of INCB050465 as follows:

- To store study treatment at room temperature.
- To remove from the study treatment bottle only the number of tablets needed at the time of administration.
- Not to remove doses in advance of the next scheduled administration.
- To make every effort to take doses on schedule.
- To report any missed doses.
- To keep INCB050465 in a safe place and out of reach of children.
- To bring all used and unused study treatment kits to the site at each visit.

5.3. Treatment Compliance

Compliance with all study-related treatments should be emphasized to the subject by the site personnel, and appropriate steps should be taken to optimize compliance during the study. Compliance with study treatment will be calculated by the sponsor based on the drug accountability documented by the site staff and monitored by the sponsor/designee (tablet counts). Subjects will be instructed to bring all study treatments with them to the study visits in order for site personnel to conduct tablet counts to assess study treatment accountability. The drug accountability documentation will be used by the sponsor to calculate treatment compliance.

5.4. Treatment Interruptions and Adjustments

5.4.1. Criteria and Procedures for Dose Interruptions and Reductions of INCB050465

Treatment with INCB050465 may be interrupted for up to 14 days to allow for resolution of toxicity. Subjects may resume treatment if no medical condition or other circumstance exists that, in the opinion of the investigator, would make the subject unsuitable for further participation in the study. The treating investigator should contact the sponsor to discuss the case of any subject whose treatment has been interrupted for more than 14 days before restarting treatment with INCB050465.

5.4.1.1. Dose Modifications

Dose modification guidance for AEs that have been previously observed in subjects receiving INCB050465 or are potential class-effect AEs are provided (see [Table 3](#) and [Table 5](#)). The starting dose and dose reduction levels of INCB050465 are provided (see [Table 4](#)). Individual decisions regarding dose interruption and reduction should be made using clinical judgment and in consultation with the sponsor's medical monitor, taking into account relatedness of the AE to the study treatment and the subject's underlying condition. Adverse events that have a clear alternative explanation or transient (≤ 72 hours) abnormal laboratory values without associated clinically significant signs or symptoms may be exempt from dose reduction guidelines

Table 3: Guidelines for Interruption and Restarting INCB050465

ADVERSE EVENT	ACTION
Chemistry	

 Grade 3 AST and/or ALT ($> 5.0 \times \text{ULN}$). 
Note: In subjects with liver metastasis-related elevations at baseline, contact sponsor to discuss clinical management and possible dose reductions.
	
Step 1: Interrupt INCB050465 and monitor weekly until the toxicity has resolved to Grade ≤ 1.
 
Step 2: Restart INCB050465 at next lower dose with medical monitor approval. Monitor as clinically indicated.

Hematology	

 Grade 3 ANC ($< 1.0 \times 10^9/\text{L}$) Grade 2 platelet count (50 to $< 75 \times 10^9/\text{L}$) for subjects who enrolled with platelets $> 100 \times 10^9/\text{L}$. Grade 3 platelet count ($< 50 \times 10^9/\text{L}$) for subjects who enrolled with platelets $\leq 100 \times 10^9/\text{L}$. 	
Step 1: Interrupt INCB050465 up to 14 days until the toxicity has resolved to Grade ≤ 1 or pretherapy baseline. For Grade 3 ANC, monitor at least weekly.
 
Step 2: Restart INCB050465 at same dose; monitor as clinically indicated.

 Grade 4 ANC ($< 0.5 \times 10^9/\text{L}$). Grade 3 or Grade 4 febrile neutropenia. Platelet count is Grade 4 ($< 25 \times 10^9/\text{L}$). 	
Step 1: Interrupt INCB050465 up to 14 days until the toxicity has resolved Grade ≤ 2. (Monitor at least weekly.)
 
Step 2: Restart INCB050465 at same dose. Monitor as clinically indicated. If recurs, restart at next lower dose.

Other toxicities	

 Diarrhea/colitis. 	See Table 5 .

 Pneumonitis (Grade 1). 	
Step 1: Interrupt INCB050465 until the toxicity has resolved.
 
Step 2: Restart INCB050465 at next lower dose. Monitor as clinically indicated.

 Pneumonitis (Grade ≥ 2). 	Permanently discontinue INCB050465.

 Skin toxicity (eg, rash, pruritus, etc, unless otherwise specified) (Grade 2 and 3). 	
Step 1: Interrupt INCB050465 until the toxicity has resolved to Grade ≤ 1.
 
Step 2: Restart INCB050465 at same dose. If assessed as related to INCB050465, restart at next lower dose.

 Exfoliative dermatitis (Grade 1). 	
Step 1: Interrupt INCB050465 until the toxicity has resolved.
 
Step 2: Restart INCB050465 at next lower dose. Monitor as clinically indicated.

 Exfoliative dermatitis (Grade ≥ 2). 	Permanently discontinue INCB050465.

 Intestinal perforation (any grade). 	Permanently discontinue INCB050465.

 PJP infection. 	Interrupt INCB050465. Permanently discontinue INCB050465 if PJP infection is confirmed.

 CMV infection. 	Subjects with CMV viremia without associated clinical signs of CMV infection should be carefully monitored. Consider interrupting INCB050465 for subjects with CMV viremia and clinical signs of infection until the infection has resolved. Restart INCB050465 reduced by 1 dose level if approved by the medical monitor.

Table 3: Guidelines for Interruption and Restarting INCB050465 (Continued)

ADVERSE EVENT	ACTION
Other toxicities (continued)	
• Varicella zoster infection.	Interrupt INCB050465. Restart INCB050465 only by approval of the medical monitor.
• Any Grade 1 or Grade 2 toxicity unless otherwise specified.	Continue INCB050465 and treat the toxicity; monitor as clinically indicated.
• Any Grade 3 toxicity, if clinically significant and not manageable by supportive care unless otherwise specified.	Step 1: Interrupt INCB050465 up to 14 days until the toxicity has resolved to Grade ≤ 1. Step 2: Restart INCB050465 at same dose. If assessed as related to INCB050465, restart at next lower dose. If interrupted for > 14 days, contact the medical monitor for approval to restart INCB050465. Monitor as clinically indicated.
• Any recurrent Grade 3 toxicity after 2 dose reductions.	Discontinue INCB050465 administration and follow-up per Protocol. Exceptions require approval of sponsor.
• Any other Grade 4 toxicity.	Discontinue INCB050465 administration and follow-up per Protocol. Exceptions require approval of sponsor.

ALT = alanine aminotransferase; AST = aspartate aminotransferase; CMV = cytomegalovirus; IV = intravenous; ULN = upper limit of normal.

Table 4: Dose Levels and Reductions for INCB050465

Timepoint	Treatment A	Treatment B
Starting dose	20 mg QD for 8 weeks (Day 1 through Day 56)	20 mg QD for 8 weeks (Day 1 through Day 56)
First dose reduction	10 mg QD	10 mg QD
Second dose reduction	5 mg QD	5 mg QD
Week 9 (Day 57) onward	20 mg once weekly ^a	2.5 mg QD ^b
First dose reduction	10 mg once weekly	1 mg QD ^c
Second dose reduction	5 mg once weekly	NA

^a All subjects will receive 20 mg once weekly at Week 9 (Day 57) regardless of prior dose level, unless a dose modification of a switch to a QW schedule before Week 9 is required for diarrhea/colitis management (see Table 5).

^b All subjects will receive 2.5 mg QD at Week 9 (Day 57) regardless of prior dose level, unless a dose modification of a switch to a QW schedule is required for diarrhea/colitis management (see Table 5).

^c Further dose modification due to diarrhea or colitis for subjects on 1 mg QD is permitted (see Table 5).

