3.1. Subject Inclusion Criteria

A subject who meets all of the following criteria may be included in the study:

1. Men and women, aged 18 or older.
2. Pathologically confirmed MCL, with documentation of either overexpression of cyclin D1 or t(11;14).
3. Have received at least 1 but no more than 3 prior systemic treatment regimens.
 - a. Subjects in Cohort 1 will have previously received ibrutinib.
 - b. Subjects in Cohort 2 will not have previously received a BTK inhibitor (eg, ibrutinib).
4. Documented failure to achieve at least PR with or documented disease progression after the most recent treatment regimen.
5. Radiographically measurable lymphadenopathy or extranodal lymphoid malignancy (defined as the presence of ≥ 1 lesion that measures > 1.5 cm in the LDi and ≥ 1.0 cm in the longest perpendicular diameter as assessed by CT or MRI).
6. Subjects must be willing to undergo an incisional, excisional, or core needle lymph node or tissue biopsy or provide a lymph node or tissue biopsy from the most recent available archival tissue.
7. Life expectancy > 3 months.
8. ECOG performance status 0 to 2 (see [Appendix B](#)).
9. Adequate hematologic, hepatic, and renal function (values must not be achieved with growth factors):
 - a. ANC $\geq 1.0 \times 10^9/L$.
 - b. Hemoglobin ≥ 8.0 g/dL.
 - c. Platelet count $\geq 50 \times 10^9/L$.
 - d. Total bilirubin $\leq 1.5 \times ULN$. Subjects with documented history of Gilbert's syndrome and in whom total bilirubin elevations are accompanied by elevated indirect bilirubin are eligible.
 - e. ALT/AST $\leq 3.0 \times ULN$ or $\leq 5 \times ULN$ in the presence of liver metastases.
 - f. Calculated creatinine clearance ≥ 50 mL/min by the Cockcroft-Gault Equation ([Cockcroft and Gault 1976](#)) or the estimated glomerular filtration rate ≥ 50 mL/min/1.73 m² using the Modification of Diet in Renal Disease formula.

10. Willingness to avoid pregnancy or fathering children based on the criteria below:
- Woman of nonchildbearing potential (ie, surgically sterile with a hysterectomy and/or bilateral oophorectomy OR ≥ 12 months of amenorrhea and at least 45 years of age).

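### Protocol Table 3 has no platelet entry for 25 to <50 × 10^9/L in subjects enrolled above 100, so the written hold rule is weaker there than at 50 to <75

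*Protocol*

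**What the plan says.** All platelet counts here are in 10^9/L. Table 3 in Protocol Section 5.4.1.1 has three platelet entries in its hematology block.

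- The first, "Grade 2 platelet count (50 to" below 75, and the second, Grade 3 below 50, are each limited by the phrase "for subjects who enrolled with platelets": above 100 for the first, at or below 100 for the second. Both call for a hold of up to 14 days until Grade ≤1 or the pretherapy level, and then "Restart INCB050465 at same dose; monitor as clinically indicated".
- The third, Grade 4 below 25, applies to everyone. It calls for a hold of up to 14 days until Grade ≤2, and then "Restart INCB050465 at same dose. Monitor as clinically indicated. If recurs, restart at next lower dose".

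None of the three makes the hold depend on clinical significance.

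Further down, Table 3 has a general row: "Any Grade 3 toxicity, if clinically significant and not manageable by supportive care unless otherwise specified". It calls for a hold of up to 14 days until Grade ≤1 and a restart at the same dose, with a qualifier: "If assessed as related to INCB050465, restart at next lower dose. If interrupted for" more than 14 days, the medical monitor must approve the restart.

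The text above the table says: "Individual decisions regarding dose interruption and reduction should be made using clinical judgment and in consultation with the" sponsor's medical monitor. Inclusion criterion 9 ("Adequate hematologic, hepatic, and renal function (values must not be achieved with growth factors") sets a platelet floor of 50 in item 9c, so subjects on both sides of 100 can enroll. Section 5.4.3 names bleeding with low platelets as a danger but gives no dosing rule.

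**The concern.** A toxicity table should not become more permissive as the toxicity worsens. For a subject enrolled above 100, the hold is unconditional at 50 to <75, conditional at 25 to <50, and unconditional again below 25. An investigator who follows the table literally would hold drug at 60. At 40, the same investigator would first have to judge the event both clinically significant and not manageable by supportive care.

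The two neutrophil entries in the same block (<1.0 and <0.5) leave no such gap, and no reason for the platelet pattern is given. It looks like a drafting omission. What is at stake is consistent handling of low platelets across sites, for a toxicity that Section 5.4.3 describes as an apparent class effect.

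**Working it through.** The plan states no figure on this point, so there is none to reproduce. The check is to see which entry applies at each count, and then how a subject can reach the uncovered band while on drug.

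**Grades, from Table 3's own cut-offs.** Grade 2 is 50 to <75 and Grade 4 is <25. Grade 3 is therefore 25 to <50, Grade ≤1 is 75 or above, and Grade ≤2 is 50 or above.

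**Which row applies.** Testing every whole-number count from 0 to 99 at enrollment counts of 150, 101, 100 and 60 gives:

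| Count | Enrolled above 100 | Enrolled at 50 to 100 |
|---|---|---|
| 75 to 99 | no hematology entry | no hematology entry |
| 50 to <75 | Grade 2 entry: hold | no hematology entry |
| 25 to <50 | **no hematology entry; general Grade 3 row** | Grade 3 entry: hold |
| <25 | Grade 4 entry: hold | Grade 3 and Grade 4 entries: hold |

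The gap is exactly 25 to <50 in subjects enrolled above 100.

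**Same count, different enrollment level.** At a count of 40:
- enrolled at 50: fall of (50 − 40)/50 = 20%, hold;
- enrolled at 100: fall of (100 − 40)/100 = 60%, hold;
- enrolled above 100: fall of more than 60%, general row only.

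The subject with the largest fall has the weakest written trigger.

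**Restart, enrolled above 100.** After 50 to <75: same dose. After 25 to <50 under the general row: same dose, or next lower dose if related. After a first <25: same dose, with a reduction only on recurrence. The general row is therefore weaker on the trigger to hold but stricter on restart after a related event.

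**How the band is reached while on drug.**
- *No earlier Grade 4 restart.* A count seen at 50 to <75 already leads to a hold until 75 or above. The gap matters when the count passes from 75 or above to below 50 between two draws, a fall of more than (75 − 50)/75 = 33.3%.
- *After Grade 4 platelets.* The Grade 4 row permits restart from 50 upward. A subject restarted at 55 who falls to 45 has dropped (55 − 45)/55 = 18%. This route takes the Grade 4 restart level as governing over the 50 to <75 hold. The Amendment 3 rationale in Appendix E, which ties that level to the eligibility criteria, supports this reading.

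**How often counts are taken.** Planned hematology is every 2 weeks to Week 8, every 4 weeks to Week 48, then every 12 weeks. The expected treatment period of 14 months is 14 × 365.25/12/7 = 60.9 weeks. That gives Weeks 2, 4, 6 and 8 (4 counts), Weeks 12 to 48 (10) and Week 60 (1), or 15 after Day 1. Four of these fall in the 20 mg daily phase and 11 in maintenance.

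**The case against.** The strongest reply is that the missing entry has little practical force. Table 3 is headed as guidelines, and every row is subject to clinical judgment in consultation with the medical monitor. Section 5.4.1 allows a hold of up to 14 days for any toxicity to resolve. Section 5.5.1 requires withdrawal for unacceptable toxicity. Table 3 stops drug for Grade 3 toxicity that recurs after two reductions. Its general instruction to continue dosing is for Grade 1 or 2 events only. Many investigators would read 50 to <75 as a floor and hold at 40 anyway. Counts are most frequent in the 20 mg daily phase. After Week 8 the average daily dose falls to 2.5/20 = one-eighth, or (20/7)/20 = one-seventh, and Section 6.6 permits unscheduled visits.

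Most of this stands, and it limits the consequence. It does not supply the missing rule: none of these provisions sets a platelet threshold, and judgment applies equally to the bands where an explicit rule was written.

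A reader might infer more than the documents support:
- *That the protocol tells sites to keep dosing at 25 to <50.* It does not. The instruction is conditional, and discretion to hold remains.
- *That the gap needs a fall of more than one third.* That holds only without an earlier Grade 4 restart.
- *That the 10% rate of new or worsening Grade ≥3 thrombocytopenia among 72 subjects in Section 1.3 sizes the problem.* That figure pools Grades 3 and 4, all enrollment counts and doses of 5 to 45 mg daily, so it cannot give the number first seen in this band.

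**Conclusion.** The gap is certain on the text: for subjects enrolled above 100, platelets of 25 to <50 have no hematology entry, and the row that catches them has a weaker trigger to hold than the rule for the milder band above. It is an error in a written safety rule and calls for a minor wording correction.

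Its practical size cannot be stated, because the documents do not split platelet events by grade, enrollment count or first observed count. Being affected requires enrollment above 100, a count of 25 to <50 reached on drug by either route, and an investigator who judges the event not clinically significant, or manageable with supportive care, and does not otherwise choose to hold. The primary response rate, power and sample size are unaffected.

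**What to change.** At the next amendment, add to the hematology block of Table 3: *Grade 3 platelet count (25 to <50 × 10^9/L) for subjects who enrolled with platelets > 100 × 10^9/L*. The action would be a hold of up to 14 days until Grade ≤1 or the pretherapy level, with no clinical-significance condition.

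State the restart rule in the same entry. The default should keep what the general row gives now: same dose, or next lower dose if related. Simply widening the existing entry to 25 to <75 would move related Grade 3 events to a same-dose restart with no reduction on recurrence. That is a separate clinical decision, to be made only if the clinical team wants it. It deserves thought for Treatment B, the regimen that SAP Section 11.2 records as selected, because Table 4 gives its maintenance phase only one reduction (to 1 mg daily), with further modification allowed only for diarrhea or colitis.

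The cost is one table entry and some additional short dose holds. Visits, sample size and analyses do not change.
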